11.1 Subject Disposition

Different variables from the CRF will be considered to determine the number of patients who reached the various stages of the study. The following counts will be reported by study group:

- Number of participants randomised
- Number of randomised participants who received study medication at least once
- Number of participants who completed the study medication.
- Number of participants who had the delivery.
- Number of participants who completed the post-delivery follow-up visit.
- Number of participants who withdrew the study before completion.

11.2 Protocol Deviations

The investigators will conduct the study in compliance with the protocol. Protocol compliance will be monitored by a monitor who will undertake site visits to ensure that the trial protocol is adhered and that necessary paperwork (CRF's, patient consent) is being completed appropriately. Any deviations from the protocol will be reported to a sponsor representative per the process and timelines communicated and reported in the final CSR report. A listing of major protocol violations (significant occurrences which may adversely affect the rights, safety or wellbeing of the participants and/or the scientific value of the trial) will be provided.

11.3 Inclusion and Exclusion Criteria

A listing will be generated showing the number and percentage of participants that fulfilled the inclusion and exclusion criteria listed in sections 8.2.2 and 8.2.3 of the Protocol.

12 Demographic and Baseline variables

12.1 Demographics

Age and race (Caucasian vs non-Caucasian) will be considered demographic variables. Mean, standard deviation, median, max and min will be reported for age, and counts and percentages will be reported for race.

12.2 Prior and Concurrent medications

Throughout the study, investigators may prescribe any concomitant medications or treatments deemed necessary to provide adequate supportive care except for those listed in Section 9.7.2 of the Protocol. Participants will be instructed to inform the investigator prior to starting any new medications. Any medication, including non-prescription medication(s) and herbal product(s), other than the study medication taken during the study will be recorded in the CRF from the date the participant signs informed consent to the last visit, except those listed below which are expected pregnancy related concomitant medications;

- a) Pain relief [entonox, pethidine, fentanyl (for epidural), bupivacaine (for epidural)]
- b) Local Anesthesia for perineal repair
- c) Prophylactic uterotonic administration or drugs for active management of the third stage of labour i.e., oxytocin (syntocinon) 10 units IM or ergometrine maleate/oxytocin (Syntometrine) 500mcg/5 units IM
- d) Ranitidine
- e) Sodium Citrate

EMERGE NUIG-2016-01, Statistical Analysis Plan Version 1, 21/03/2023

- f) Routine vaccines in the baby (BCG/TB, Diphtheria, Tetanus, Pertussis, Haemophilus Influenza B (Hib), Polio, Hep B, Pneumococcal (PCV), Meningococcal (Men B))
- g) Maternal vaccinations
- h) Vitamin K administration (baby only)
- i) Anti D for mother
- j) Over-the-counter antenatal multivitamins

A listing of the prior and concurrent medications will be provided as an appendix in the CSR.

12.3 Baseline and Screening Conditions

Social history (smoking and alcohol), previous pregnancies, current pregnancy, vital signs, glucose tolerance test results, history of gastrointestinal events, lab test results, standard care (dietary and physical exercise advice) received, socioeconomic status and EQ5D-5L questionnaire responses will be summarised. Numerical values will be summarised using the mean, standard deviation, median, minimum and maximum, while categorical values will be summarized using counts and percentages.

A listing of all Diseases/Conditions will be provided for the analysis of the medical history. If possible, the most common conditions will be summarized using counts and percentages.

12.4 Treatment Compliance

The date, pack number and number of tablets dispensed is recorded at screening and drug accountability is documented at Weeks 2, 4, 6, 8, 10 and 12. Drug dispensation and return (along with expected consumption and adherence) are recorded at weeks 4, 8, 12, with the final date and quantity of drugs returned recorded at 12 weeks post-partum.

Non-compliance is defined as less than 80% drug adherence of the participant's maximum tolerated dose. These data will be shown in a listing and summary table (per visit and overall).

13 Efficacy Analyses

13.1 Primary Efficacy Analysis

The primary efficacy outcome is a composite of:

- Insulin initiation (Yes/No) or
- Fasting hyperglycemia ≥ 5.1 mmol/l at week 32 or 38.

Suitable numerical and graphical techniques will be used to compare the primary and secondary responses and the balance in explanatory variables at baseline. The primary analysis will be a two-sample comparison of reduction in the proportion of women needing insulin between treatment and control arms. A logistic regression model will be used to adjust for the stratifying variables, BMI and past history of GDM, along with other patient characteristics as appropriate.

A small number of participants (24) were randomised in more than one occasion for this study, each corresponding to a new pregnancy (49 in total). Note that the primary analysis described above will treat these duplicated pregnancies as independent. Although it is not expected that this issue will be influential in the overall conclusions derived from the analysis of the primary outcome, a sensitivity analysis will be performed considering only the first pregnancy per woman, among the 24 women who entered the study more than once.

A secondary exploratory analysis will involve a comparison of the time to insulin initiation between the treatment groups, initially using the log-rank test and then the proportional hazards model in order to adjust for patient characteristics as appropriate. Longitudinal data analyses based on linear mixed models will be used to evaluate the effect of intervention on secondary outcome of mean change in weight (from baseline to postpartum follow-up).

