Methodology	
The study will comprise 3 periods; 1) screening, 2) treatment, and 3) follow up.
 
During screening, informed consent will be obtained and evaluations of the participant's eligibility will be performed. At the beginning of the treatment period, participants will be randomised up to 28 weeks gestation (+ 6 days) in a 1:1 ratio, stratified by BMI and previous GDM to receive either metformin or matching placebo, in addition to usual care. The treatment period will be until delivery. Participants will be followed up at 4 weeks post-partum (+/- 7 days) by telephone, and 12 weeks postpartum (+/- 4 weeks) in the clinic for maternal and neonatal outcomes.

Statistical methods	
The primary analysis will be a comparison of the incidence of the composite primary outcome of proportion of participants needing insulin or fasting blood glucose ≥ 5.1 mmol/l at gestational weeks 32 or 38 between treatment and control arms, using an exact test for a binomial response. A secondary analysis will involve a comparison of the time to insulin initiation between the treatment groups, using the log-rank test and the proportional hazards model.

Health Economic Analysis	
The health economic analysis will consist of trial-based economic evaluation and will incorporate both cost effectiveness analysis and cost utility analysis to compare the alternative treatment strategies: 1) metformin in addition to usual care for GDM and 2) usual care for GDM.

313

314

315

316 **5. ABBREVIATIONS**

317

318	ACOG	American Congress of Obstetrics and Gynaecologists
319	ADA	American Diabetes Association
320	AE	Adverse event
321	ALT	Alanine Aminotransferase
322	ANOVA	Analysis of Variance
323	APH	Antepartum haemorrhage
324	AR	Adverse reaction
325	AST	Aspartate Aminotransferase
326	b.i.d.	Twice daily
327	BCSH	British Committee for Standards in Haematology
328	BMI	Body mass index
329	CDMS	Clinical data management system
330	CI	Confidence interval
331	CRF	Case report form
332	CRFG	Clinical Research Facility Galway

333	CT	Clinical trial
334	CTA	Clinical trial authorisation
335	DNS	Diabetes Nurse Specialist
336	DMF	Data management file
337	DOB	Date of birth
338	DTSQ	Diabetes Treatment Satisfaction Questionnaire
339	DSMB	Data safety and monitoring board
340	DSUR	Development safety update report
341	EBCOG	European Board and College of Obstetrics and Gynaecology
342	e-CRF	Electronic case report form
343	EDC	Electronic data capture
344	EDTA	Ethylenediaminetetraacetic acid

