1319 Influenza B (Hib), Polio, Hep B, Pneumococcal (PCV), Meningococcal (Men B)
1320 g) Maternal vaccinations
1321 h) Vitamin K administration (baby only)
1322 i) Anti D for mother
1323 j) Over-the-counter antenatal multivitamins

1324 1325 9.7.1. Permitted Medications/Non-Investigational Medicinal Products

1326 The following medications are permitted for routine use throughout the duration of the trial:
1327
1328 1. Paracetamol
1329 2. Aspirin
1330 3. Low molecular weight heparin
1331 4. Antihypertensives
1332 5. Routine pregnancy supplements
1333 6. Folic Acid
1334 7. Vitamin D
1335 8. Antacids
1336 9. Prescribed medications for established chronic diseases
1337 10. Insulin

1338 Insulin taken for less than 72 hours will be recorded but will not be considered a primary outcome
1339 measure.

1340 9.7.2. Prohibited Medications

1341 The following medications are not permitted for routine use throughout the duration of the trial:

1342
1343
1344
1345
1346
1347 • Non-study oral hypoglycaemic medications
1348 • Intravascular contrast studies with iodinated materials

1349
1350 Intravascular contrast studies with iodinated materials can lead to acute alteration of renal function
1351 and have been associated with lactic acidosis in patients receiving metformin. Metformin/placebo
1352 must be discontinued prior to or at the time of the imaging procedure and not restarted until at least
1353 48 hours after, provided that renal function has been re-evaluated and found to be stable.

1354
1355 If for any clinical reason the patient requires treatment with any of the above, the patient must
1356 discontinue study treatment either temporarily or permanently and this must be documented in the
1357 CRF.
1358

1359 **9.7.3. Cautionary Medications**

1360
1361 Some medicinal products, such as NSAIDs (including selective cyclo-oxygenase (COX) II inhibitors),
1362 ACE inhibitors, angiotensin II receptor antagonists and diuretics (particularly) loop diuretics) may
1363 adversely affect renal function and may increase the risk of lactic acidosis. When starting or using
1364 such products in combination with metformin/placebo, monitoring of renal function may be required.
1365
1366 Medicinal products with intrinsic hyperglycaemic activity (e.g. systemic or local glucocorticoids and
1367 sympathomimetics) may require more frequent blood glucose monitoring.
1368
1369 As metformin is a substrate of the OCT1 and OCT2 organic cation transporters, co-administration with

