1779 number of strategies to enhance follow-up for this outcome (e.g. home monitoring of weight).
1780

1781 11.3. Analysis Sets

1782 11.3.1. Intention-to-Treat Analysis Set

1783 The intention-to-treat analysis set, also termed full analysis set in the International Conference on
1784 Harmonization (ICH) E9 guideline, will include all randomized participants.
1785

1786 11.3.2. Safety Analysis Set

1787 The safety analysis set will include all randomized participants who received at least one dose of
1788 study medication.
1789

1790 11.4. Demographic and baseline disease characteristics

1791 Demographic and baseline characteristics of the study population will be summarized using graphical
1792 displays and descriptive statistics for each treatment group.
1793

1794

1800 **11.5. Effectiveness Analysis**

1801

1802 Suitable numerical and graphical techniques will be used to compare the primary and secondary

1803 responses and the balance in explanatory variables at baseline. The primary analysis will be a two-

1804 sample comparison of reduction in the proportion of participants needing insulin between treatment

1805 and control arms using an exact test for a binomial response.

1806

1807 We will also conduct a logistic regression analysis, to adjust for differences of baseline co-variates

1808 between treatment groups. Several strategies for including explanatory variables will be employed

1809 where penalisation for multicollinearity will be achieved using ridge penalties. Following this the most

1810 parsimonious subset of predictor variables will be identified using computationally intensive data

1811 driven techniques such as the classification trees and the Lasso penalty.

1812

1813 A secondary exploratory analysis will involve a comparison of the time to insulin initiation between the

1814 treatment groups, initially using the log-rank test and then the proportional hazards model in order to

1815 adjust for patient characteristics as appropriate. Repeated measures ANOVA will be used to evaluate

1816 the effect of intervention on secondary outcome of mean change in weight (from baseline to post-

1817 partum follow-up).

1818

1819 **11.5.1. Primary Effectivness Outcomes**

1820

1821 The primary efficacy outcome is a composite of:

1822

- Insulin initiation (Yes/No)
- Fasting glucose value <5.1 mmol/l and ≥ 5.1 mmol/l

1823

1824 **11.5.2. Secondary Effectiveness Outcomes**

1825

1826 Secondary efficacy outcomes include:

1827

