GDM results from reduced insulin sensitivity and/or reduced insulin production. Metformin increases insulin sensitivity and thus it has the potential as a treatment option for GDM. Metformin is weight neutral and is not associated with hypoglycaemia, two factors that increase its acceptability for pregnancy, and an advantage over insulin. Metformin has been shown to be safe in pregnancy (for mother and baby), when it is introduced after the failure of diet and exercise. However, in many countries (including Ireland), insulin therapy remains the standard of care for the treatment of GDM, in women who have failed to achieve normoglycemia after diet and exercise. Distinct from previous clinical trials, we plan to evaluate the use of metformin (compared to placebo) at the time of initial GDM diagnosis (i.e. at the same time as diet and exercise interventions), and evaluate its use in all women with GDM and not just those with elevated Body Mass Index (BMI).

The EMERGE trial will evaluate metformin introduced at the time of GDM diagnosis in women of all BMI categories, to determine whether treating all patients with GDM (rather than just those who fail Medical Nutritional Therapy (MNT) / exercise) results in better outcomes for mothers and babies. The primary outcome is the development of hyperglycemia, represented as the composite of a) initiation of insulin (as this reflects clinically meaningful hyperglycemia) and a venous fasting glucose measurement $>5.1\text{mmol/l}$ at weeks 32 and 38 of gestation. Secondary outcome measures include excessive Gestational Weight Gain (GWG), and neonatal and maternal outcomes. Finally, we will conduct an extensive cost-benefit and cost-utility analysis of metformin use in GDM pregnancy. Results of the EMERGE trial may considerably impact on clinical practice by providing evidence to support early active management with metformin at the time of diagnosis in a broader GDM population.

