5.1 Study objectives

5.1.1 Primary Objective

The primary objective is to determine if metformin reduces (a) the requirement for insulin or (b) the rate of fasting maternal hyperglycaemia (≥ 5.1 mmol/l) at gestational weeks 32 and 38.

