5.2 Study endpoints

5.2.1 Primary endpoint

A composite primary outcome of insulin initiation or fasting hyperglycemia (glucose ≥ 5.1 mmol/l) on study specific fasting laboratory glucose at gestational weeks 32 or 38 will be used. This approach allows us to measure 'treatment failure' in two discreet ways. The introduction of insulin reflects clinically meaningful hyperglycaemia, and is measured at any time during clinical trial. In addition, a standardised fasting glucose will be completed at gestational weeks 32 and 38, to capture additional participants who have fasting hyperglycaemia but have not had insulin introduced during the clinical trial.

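### The primary test is written for insulin use alone, but the primary outcome is insulin or fasting hyperglycaemia

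*SAP*

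**What the plan says.** **The outcome.** SAP 5.2.1 specifies "A composite primary outcome of insulin initiation or fasting hyperglycemia". SAP 13.1 lists two components joined by 'or': insulin initiation (Yes/No), and "Fasting hyperglycemia ≥ 5.1 mmol/l at week 32 or 38". Protocol 7.3.1 gives the same composite, and Protocol 11.5.1 lists both components.

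**The test.** The next paragraph of SAP 13.1 reads: "The primary analysis will be a two-sample comparison of reduction in the proportion of women needing insulin between treatment and control arms". The logistic regression sentence that follows names no response. Protocol 11.5 also describes a two-"sample comparison of reduction in the proportion of participants needing insulin between treatment" and control arms, using an exact test. The Protocol synopsis differs: it plans a "comparison of the incidence of the composite primary outcome of proportion of participants needing insulin or fasting blood glucose" at or above 5.1 mmol/l.

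**The components.**
- SAP 3 (Preface) describes the composite as "initiation of insulin (as this reflects clinically meaningful hyperglycemia) and a venous fasting glucose measurement" above 5.1 mmol/l, at weeks 32 and 38.
- SAP 5.1.1 uses at least 5.1 mmol/l "at gestational weeks 32 and 38".
- SAP 5.2.1 and 13.1 use at least 5.1 mmol/l at week 32 or 38.
- Protocol 9.7.1 adds: "Insulin taken for less than 72 hours will be recorded but will not be considered a primary outcome" measure. The SAP does not repeat this rule.

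**The concern.** The glucose component is there to pick up women with fasting hyperglycaemia who never start insulin; SAP 5.2.1 says so. A comparison of insulin use alone drops exactly these women. An analyst who follows SAP 13.1 literally would report an insulin-only p-value as the trial's primary result, and one who follows the Protocol synopsis would report a composite p-value. The SAP does not say which governs, so the choice could be made after both are known.

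The inconsistent component wording has the same effect on a smaller scale, because each variant can reclassify participants. Requiring both components, or hyperglycaemia at both weeks, gives fewer events than the 'or' forms. A value of exactly 5.1 mmol/l counts under one threshold and not under the other. An unqualified Yes/No insulin item counts courses of a day or two that the Protocol excludes.

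**Working it through.** **1. Which passages tie a test to which response**

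| Place | Response | Test named |
|---|---|---|
| Protocol synopsis | composite | exact test |
| Protocol 11.5 | insulin only | exact test |
| SAP 8.2 | composite | none |
| SAP 13.1, comparison | insulin only | two-sample comparison |
| SAP 13.1, regression | not stated | logistic model |

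No SAP passage names a test with the composite as its response.

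**2. The sample size also concerns insulin only**

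Inputs (Protocol 11.2, SAP 7): insulin 40% versus 28%, alpha 0.05 (taken as two-sided), 80% power, 1:1 allocation, 5% drop-out. The two-proportion formula gives 488 evaluable, or 520 with continuity correction, and 520/0.95 = 547.4, so 548. The other stated input, 35% with a 33% relative reduction (35% versus 23.45%), also gives 520 corrected and 548. The planned 550 is therefore reproduced from insulin rates. The cut to 535 in SAP 8.1 rests on the overall proportion taking insulin; the updated rates are not given, so 535 cannot be reproduced.

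**3. How far the two responses can diverge**

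The documents give no composite rate, so the glucose rates below are assumptions. Analysed number: 535 × 0.95 / 2 = 254 per arm.

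Composite = p + (1 − p) × f, where p is the insulin rate and f is the fasting-hyperglycaemia rate among women not on insulin.

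Power = Φ[(d − 1.96·s0)/s1], with d the difference in proportions, p̄ the mean of the two proportions, s0 = √(2p̄(1−p̄)/n) and s1 = √((p1(1−p1)+p2(1−p2))/n).

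*Scenario (a): insulin 40% versus 28%, f = 25% in both arms.*
- Insulin alone: d = 0.12, s0 = 0.0420, s1 = 0.0417. (0.12 − 0.0824)/0.0417 = 0.90; power 82%.
- Composite: 0.40 + 0.60 × 0.25 = 55%; 0.28 + 0.72 × 0.25 = 46%. d = 0.09, s0 = 0.0444, s1 = 0.0442. (0.09 − 0.0870)/0.0442 = 0.07; power 53%.
- With f at 10%, 20% and 30%, composite power is 70%, 58% and 48%.

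*Scenario (b): insulin 40% in both arms, f = 30% versus 15%.*
- Insulin alone: difference 0, so a significant result occurs only at the 5% error rate.
- Composite: 0.40 + 0.60 × 0.30 = 58%; 0.40 + 0.60 × 0.15 = 49%. d = 0.09; power 53%.

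*Favourable case, 275 per arm (550 before drop-out).* With a composite control rate of 50% to 70%, a 12-point reduction has 80% to 84% power, and a 33% relative reduction has 98% to over 99%.

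**The case against.** The best counter-argument is that the composite is plainly intended and the insulin-only sentence is leftover wording. The synopsis tests the composite, SAP 8.2 speaks of analysing the primary outcome of insulin or hyperglycaemia, SAP 13.1 opens with the composite, and Protocol 11.5.1 lists it. That is probably right about intent. It does not remove the defect: SAP 8.2 names no test, the SAP is the later and more detailed document, and the insulin-only basis of the sample size lends support to the literal reading.

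Some of the wording differences are also open to a milder reading. The 'and' in the SAP preface may merely list components, and weeks 32 and 38 may describe the blood-draw schedule. 'At any time' concerns when insulin starts, not how long it lasts; Protocol 7.3.1 uses the same idea alongside the 72-hour rule, and the SAP directs readers to the Protocol. These points reduce the weight of the secondary inconsistencies. But the preface threshold does differ, and the SAP derivation, applied as written, would count short courses.

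The power figures are illustrations. Other assumptions favour the composite, and in scenario (b) the composite would reach significance only about half the time. The divergence is between significant and non-significant results, not between effects in opposite directions. Removing 5% for drop-out is also a simplification, since SAP 9.1 analyses everyone randomised.

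**Conclusion.** The concern holds. As written, the primary comparison in SAP 13.1 and Protocol 11.5 tests one component of the primary outcome and contradicts both the outcome definition and the synopsis. The contradiction is established from the text and rests on no assumption.

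Its size cannot be fixed from the documents. With 254 per arm and the assumed rates in scenario (a), power is about 82% for insulin alone and 53% for the composite; other assumptions take composite power from about 50% to over 99%. The two responses are therefore not interchangeable. Because this concerns the response variable of the confirmatory test, it must be corrected. The differences in component wording and the missing 72-hour rule are secondary but belong in the same correction.

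**What to change.** 1. In SAP 13.1 and Protocol 11.5, replace the proportion needing insulin with the proportion meeting the composite primary outcome. Name the composite as the response of the logistic model too, and state whether the two-sample comparison or the adjusted model supplies the primary p-value.
2. Use one definition throughout: insulin initiation, with the Protocol 9.7.1 72-hour rule written into the SAP derivation, or study fasting venous glucose of at least 5.1 mmol/l at the week 32 draw or the week 38 draw.
3. Correct SAP 3 and SAP 5.1.1 to match.
4. Report insulin use alone as a secondary component analysis.
5. Beside the sample size, state that it was built on insulin rates, and give the composite rates assumed.

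The cost is SAP and Protocol wording; no new data are needed. The change should be made before the randomisation codes are used for the analysis described in SAP 8.2.

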10.6 Planned Subgroups, Interactions, and Covariates

Variation of treatment effects for primary outcome induced by baseline/demographic variables will be explored using interaction analysis. Relevant variables will be race (Caucasian vs non-caucasian), age (<30 years vs \geq 30 years), previous GDM (Yes/No) and whether this is the participant's first pregnancy.

11 Study Subjects

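### SAP 13.1: the supportive logistic model for the primary outcome has an open covariate list and does not name baseline fasting glucose, giving up precision in the adjusted estimate

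*SAP*

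**What the plan says.** SAP 13.1 defines the primary outcome as insulin initiation or fasting glucose of at least 5.1 mmol/l at week 32 or 38. It then states: "The primary analysis will be a two-sample comparison of reduction in the proportion of women needing insulin between treatment and control arms". The next sentence adds a logistic regression model to "adjust for the stratifying variables, BMI and past history of GDM, along with other patient characteristics as appropriate". No further list, selection rule or role for the model follows, and the form of BMI (continuous or cut at 30) is not given.

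The protocol names the test and comes nearest to giving the model a role. The synopsis has the comparison "between treatment and control arms, using an exact test for a binomial response", and Protocol 11.5 likewise compares treatment "and control arms using an exact test for a binomial response". Protocol 11.5 continues: "We will also conduct a logistic regression analysis, to adjust for differences of baseline co-variates". It names no covariates. It applies ridge penalties and then looks for a parsimonious subset by data-"driven techniques such as the classification trees and the Lasso penalty". The SAP is silent on that selection step.

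Fasting glucose is part of the OGTT that establishes eligibility (Protocol 8.2.2, 8.4.4) and is scheduled again at randomisation (Protocol 8.4.5, SAP 14.5). The SAP uses baseline glucose for summaries (12.3) and for changes from baseline (14.5). SAP 10.6 has covariates in its heading but lists only variables for interaction with treatment: "Relevant variables will be race (Caucasian vs non-caucasian), age", then "previous GDM (Yes/No) and whether this is" the woman's first pregnancy. BMI is not among them.

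**The concern.** Two things are at stake, both in the adjusted estimate.

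The first is precision. The trial already collects the baseline value of one of the two components of its primary outcome. A baseline measure of the quantity that later defines failure is an obvious candidate to predict it, and adjusting for a prognostic baseline variable sharpens the estimate of treatment effect. The plan names BMI and past GDM but not this variable.

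The second is whether the analysis can be checked. With an open list in the SAP and data-driven selection still standing in the protocol, a reader of the report cannot tell whether the adjusted result is the one that was planned. SAP 8.2 has an independent statistician analyse the primary outcome with the randomisation codes before database lock, so the list has to be settled before that analysis.

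**Working it through.** **1. The plan's own figure.** Inputs from SAP 7: 40% v 28%, alpha 0.05 (taken as two-sided), 80% power, 5% drop-out, 8% non-adherence.

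n per arm = [1.96·√(2·0.34·0.66) + 0.842·√(0.40·0.60 + 0.28·0.72)]² / 0.12² = 243.4, so 244 per arm and 488 in total. 488/(0.95 × 0.92) = 559, within 2% of the stated 550. This calculation compares two proportions and does not involve the adjusted model.

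**2. Evaluable number.** SAP 8.1 reduces the total to 535. 535/2 × 0.95 = 254 per arm.

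**3. The deciding test.** Taking the protocol's exact test as two-sided Fisher and enumerating all outcomes at 254 per arm:

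| Rates | Fisher power |
|---|---|
| 40% v 28% | 79.2% |
| 40% v 28.96% (8% of the metformin arm at the control rate: 0.92 × 28 + 0.08 × 40) | 71.6% |
| 50% v 38% | 75.8% |
| 60% v 48% | 74.7% |

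The 40% and 28% are insulin-only rates. The documents give no composite rate, so the last two rows are assumptions.

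**4. The adjusted model with and without glucose.** The documents give no prognostic strength for fasting glucose, so a range is used. Each scenario has 4,000 simulated trials, paired Wald tests and marginal event rates held fixed. Assumptions: BMI above 30 in 40% of women and previous GDM in 25%, each with an odds ratio of 1.5; standardised glucose with correlation 0 or 0.3 with BMI. At 40% v 28% the model with BMI and past GDM alone has 81–83% power. The gain in percentage points from adding glucose is (correlation 0 / 0.3):

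| OR per SD | 40 v 28% | 50 v 38% | 60 v 48% | 40 v 28.96% |
|---|---|---|---|---|
| 1.0 | -0.2 / 0.0 | 0.3 / -0.1 | 0.0 / 0.0 | 0.0 / -0.1 |
| 1.2 | 0.3 / 0.3 | -0.1 / 0.3 | 0.3 / 0.4 | 0.0 / 0.2 |
| 1.65 | 1.6 / 2.3 | 2.4 / 2.1 | 2.6 / 2.8 | 2.1 / 3.1 |
| 2.2 | 4.2 / 3.5 | 5.3 / 4.6 | 4.5 / 3.9 | 5.3 / 3.6 |
| 3.0 | 7.0 / 6.0 | 7.6 / 7.3 | 8.5 / 7.4 | 7.9 / 7.4 |

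The 95% simulation error is 0.2 to 1.1 points, so the small negative entries are noise. At 40% v 28% and an OR per SD of 3.0 the model reaches 89–90%.

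**5. What happens to the odds ratio.** The crude odds ratio for 40% v 28% is (0.28/0.72)/(0.40/0.60) = 0.583. At an OR per SD of 3.0 the mean estimate moves from 0.57–0.58 (BMI and past GDM) to 0.50–0.51 (with glucose), for the same 12-point risk difference. This is non-collapsibility of the odds ratio, not a larger treatment effect.

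**6. Treatment by BMI.** The variance of the main-effect log odds ratio is V = 1/(254·0.40·0.60) + 1/(254·0.28·0.72) = 0.0359. With a share f of women above BMI 30, the interaction has SE = √(V/[f(1−f)]), which is 0.387 at f = 0.4. For an interaction as large as the main effect (|log OR| = 0.539) the power is 28.6%. Over f = 0.3 to 0.5 and the three 12-point scenarios it is about 24–30%.

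**The case against.** The strongest reply is that none of this touches the result that decides the trial. SAP 13.1 attaches the label of primary analysis to the two-sample comparison, the synopsis names only the exact test, and Protocol 11.5 introduces the logistic model as something done in addition. That stands. A reader might infer from the silence in SAP 13.1 that the model competes with the two-sample test, or that the open list could move the deciding p-value. Read together, the documents do not support this. If the smallest p-value over all covariate subsets were reported, the adjusted model's type I error could reach 7.6–14.1% (three to five extra covariates, OR 1.5–2.0 per SD). That is a worst case for a supportive analysis, not a forecast.

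A second reply is that the gain rests entirely on assumed odds ratios and is negligible at 1.2. This also stands. It limits the size of the point but not its direction, since nothing material is lost when glucose is not prognostic.

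A third is that comparing 79.2% for the exact test with 81–83% for the model flatters adjustment. Correct: an uncorrected chi-square test has about 82% power at 40% v 28%, so most of that gap is Fisher's conservatism. The gains in the table are model against model and are not affected.

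A fourth is that the response is itself unclear: SAP 13.1 defines a composite, but its comparison sentence mentions only insulin. For insulin alone, the case for glucose as a component's own baseline is weaker. The fix should therefore name the response.

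Finally, the all-BMI rationale in Protocol 6.2 may suggest that omitting treatment by BMI leaves an objective unanswered. It does not: the rationale describes the population, and no listed objective concerns differences in effect by BMI.

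**Conclusion.** The point holds as an improvement to a supportive analysis. The adjusted model's covariates are only partly fixed, data-driven selection in the protocol has not been withdrawn, and the baseline value of the outcome's glucose component is not named. The omission causes no bias. It gives up about 0 to 7 points of power in the adjusted model at 40% v 28%, and up to 8.5 points at the other assumed rates, for ORs per SD of 1.0 to 3.0. The power of the deciding comparison is unchanged.

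The size depends on the assumed prognostic strength, the assumed BMI and GDM distributions, and 254 evaluable women per arm. That there is no material loss at an OR of 1.0 held in every scenario.

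A reader might go further and conclude that the adjusted model should become the deciding analysis. The documents do not call for that. It would depart from the test named in the protocol and from the two-proportion basis of the sample size, after the look at accruing data described in SAP 8.1. Treatment by BMI is an optional exploratory estimate with low power.

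**What to change.** Before the randomisation codes are used (SAP 8.2), amend SAP 13.1 as follows:

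- Name the composite as the response of the adjusted model.
- Fix the covariates as BMI (stating continuous or cut at 30), previous GDM and continuous baseline fasting glucose, and delete the open-ended clause.
- Take glucose from one source for all women. The OGTT fasting value should be nearly complete because eligibility requires the OGTT. Mixing it with the randomisation sample is less clean: women receive diet and exercise advice after a positive OGTT, and randomisation may follow screening by up to 7 days (Protocol 8.3.1).
- State that the tree and Lasso selection of Protocol 11.5 will not be used for the treatment effect.
- Report a marginal risk difference or risk ratio from the model alongside the odds ratio.
- State that the two-sample comparison decides and the adjusted model is the key supportive analysis.

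Optionally, add treatment by BMI to SAP 10.6 as an exploratory estimate with its confidence interval and a note on low power.

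The cost is SAP wording; no new data are needed and the deciding test is untouched. The one downside is that the conditional odds ratio will lie further from 1 than the unadjusted one, which the marginal effect addresses.
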